In addition to those reviewed above, a larger number of proteins have been implicated in fear conditioning and extinction, including components of the MAPK and PI-3 kinase intracellular signaling cascades (Lin et al., 2003), the dopamine D1 receptor (Pickel et al., 2006), calcineurin (Lin et al., 2003), gephyrin (Chhatwal et al., 2005), AMPA glutamatergic receptors (Barad, 2005), and GABA(A) receptors (Davis & Myers, 2002). However, for this initial study of genetic influences on extinction learning and DCS augmentation, we believe it is prudent to limit multiple testing and Type I error by pursuing a focused analyses of a core set of extinction-related genes. Thus, we will examine key NMDA receptor-related genes (*GRIN1*, *GRIN2A*, *GRIN2B*, *DAAO*, *DAOA*) and extinction-related neuropeptides (*BDNF*, *NTRK2*, *CNR1*). Future studies in larger samples may permit analysis of a wider net of potentially relevant genes.

2. Specific Aims

Primary Aim:

The purpose of the proposed study is to conduct a double-blind, placebo-controlled trial of DCS augmentation of ERP in patients with BDD. Specifically, we intend to treat 50 BDD patients who will receive either DCS (100mg, n=25) or placebo (n=25) one hour before 8 of 10 behavior therapy sessions. We anticipate that some participants who sign consent for the study will be deemed ineligible after the initial screening visit. Consequently, our enrollment goal is 80 in order to reach our goal of 50 individuals who begin treatment.

We hypothesize that patients receiving DCS will show significantly more improvement in BDD symptoms, compared to patients receiving placebo. We intend to conduct the proposed study to collect sufficient pilot data to apply for an externally funded larger-scale research project.

Secondary Aim:

This treatment study also provides us with the opportunity to further explore the molecular genetics of BDD, as well as the genetic predictors of response to an extinction-based treatment. We will take a hypothesis-driven approach by focusing on genes and systems previously shown to mediate fear acquisition and NMDA-dependent extinction learning including NMDA-related glutamatergic loci (*GRIN1*, *GRIN2A*, *GRIN2B*, *DAAO*, *DAOA*) and three other genes strongly implicated in fear extinction (*BDNF*, *NTRK2*, *CNR1*). Other loci of interest in the molecular genetics of BDD include: the serotonin transporter gene, dopamine, GABA-A, and cytochrome P450 genes

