(7) Brown Assessment of Beliefs Scale (BABS) This reliable and valid 7-item semi-structured clinician-administered interview, assesses current delusional thinking categorically and dimensionally (Eisen et al., 1998). Excellent interrater and test-retest reliability (ICC for total score=.96 and .95), internal consistency (Cronbach's alpha=.87), convergent validity (r 's=.56-.85 with measures of delusional), and divergent validity ($r=.20$ with the

BDD-YBOCS [158]) have been demonstrated (Eisen et al., 1998). The cutpoint for the presence of delusional thinking in BDD had a sensitivity of 100% and a specificity of 86%, and it correctly identified 90% of 20 participants as delusional or nondelusional (Eisen et al., 1998). It is also sensitive to change (Phillips et al., 1998).

(8) Multidimensional Body-Self Relations Questionnaire (MBSRQ) While the BDD measures include some assessment of body image, we will also use a standard body image scale that is not specific to BDD and which assesses body image more broadly. The MBSRQ is a widely used 69-item self-report scale that assesses 3 domains of attitudes towards one's body, including appearance (Cash, 1994). Test-retest reliability ($r=.91$) and internal consistency ($\alpha=.88$) are good; concurrent validity ($r=.66$) is acceptable.

(9) Beck Depression Inventory II (BDI II); Beck, Steer & Brown, 1996). The BDI II is a 21-item self-report inventory that measures the severity of depression.

(10) Young Schema Questionnaire (YSQ) This 75-item self-report scale (Young & Brown, 1990) assesses the following areas of maladaptive schemas: emotional deprivation, abandonment, mistrust/abuse, social isolation, defectiveness/shame, failure to achieve, functional dependence/incompetence, vulnerability to harm and illness, enmeshment, subjugation, self-sacrifice, emotional inhibition, unrelenting standards, entitlement, and insufficient self-control/self-discipline. It has high internal consistency and discriminant validity (Waller et al., 2001). This scale will assess core beliefs and schemas as potential mechanisms underlying change, as several of these (e.g., defectiveness/shame) appear particularly relevant to BDD.

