Primary analyses: Our primary hypothesis is that ERP in combination with DCS is more effective than ERP in combination with a placebo. To measure this, the BDD-YBOCS will be the primary outcome measure. The main analyses will compare the two patient groups at mid-treatment and post-treatment using analysis of variance (ANOVA) and analysis of covariance (ANCOVA, controlling for BDD-YBOCS-pretreatment scores). To further determine the clinical significance of these findings, we will use the Jacobson and Truax (1991) formula to calculate the percentage of patients who fulfill the criteria for reliable and clinically significant change in each treatment condition at mid-treatment and post-treatment. Fisher's exact test for differences in frequencies of responders between the two patient groups will be performed. We will further compare the two groups at the 1- and 6-month follow-up assessments.

Power analysis: A power analysis with a sample size of 25 per group and $p < .05$ reveals that this study will convey 80% power to detect a group difference in post-treatment BDD-YBOCS scores of $d = 0.78$, which is a large effect size. Moreover, we will estimate between-group effect sizes of this pilot study to be used in designing future studies.

Secondary analyses: We hypothesize that patients who receive DCS augmentation will have greater improvement on the CGI-I, BDI, BDD-SS, and Disability Inventory at mid-treatment, post-treatment and 1- and 6-month follow-up assessments than patients who receive the placebo. ANCOVAs (controlling for pretreatment scores) and multivariate ANCOVAs (MANCOVAs) will be used for these analyses as described above, and effect sizes will be computed. Furthermore, the Cognitive and Behavioral Change Measures will be used to identify in more detail within which session, or between which sessions, any changes occurred.

Predictors of outcome: We also wish to evaluate whether ERP in combination with DCS is particularly effective or ineffective for different symptoms (as measured by the BDD Symptom Scale), attitudes (i.e., patient's judgments about the credibility of the treatment, as measured by the Expectancy Rating), or comorbid problems (e.g., depression). These factors will be included in regression analyses. We also intend to explore the relationship between minority status and treatment outcome; however, power will be limited given the small sample size.

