Mechanisms of improvement: We are also interested in potential mechanisms of change during treatment. These can be tested with multiple regression procedures via hierarchical regression models. Treatment group (DCS vs. placebo) will be the independent variable, changes in BDD symptom severity (BDD-YBOCS) the dependent variable, and, for example,

changes in beliefs as measured by the Schema Questionnaire will be the mediator. We will follow the procedures for establishing statistical mediation outlined by Baron and Kenney (1986), using residual gain scores as the measure of change in both the dependent variable and the mediator (Cohen, 1983). These residual scores will give a reliable estimate of changes in symptom severity and beliefs independent of differences in baseline severity. We will interpret our results with caution because the absence of statistical significance may reflect the somewhat limited power with only 50 patients.

Genetic Analyses: We will use quantitative trait association analytic methods to examine whether alleles and/or haplotypes of the loci selected for analyses are associated with outcome of ERP with or without DCS. Analyses will be conducted in two stages. The initial analyses will examine whether any of the genetic variants are associated with ERP outcome indexed by change in BDD-YBOCS score from baseline (at end of treatment and at 1-month and 6 month follow-up). The analyses will include a main effect analysis of each genetic variant as well as a gene x treatment interaction analysis, to examine whether allelic effects on outcome differ by treatment condition (DCS vs. placebo). If evidence of interaction is detected, we will also examine allelic effects within treatment group. For example, we expect that genes involved in NMDA receptor function (e.g. the *GRIN1* gene whose product includes the glycine (DCS) binding domain) may mediate response to DCS.

In the second stage, genetic predictors demonstrating univariate association will be entered into a multivariable linear regression model along with other predictors of treatment response in an effort to build a model that parsimoniously explains the greatest proportion of variance in response to ERP (with and without DCS). For genes in which more than one polymorphism shows evidence of association, we will select the SNP with the minimum p value to enter into the multivariable model.

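### Mediation is to be judged by the causal-steps procedure with no estimate or interval for the indirect effect; if a significant total effect is required, true mediation is missed more often at the same N = 50

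*Combined protocol and SAP*

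**What the plan says.** The combined protocol and SAP, section 6 (Mechanisms of improvement), plans hierarchical regression with treatment group as independent variable and change in BDD-YBOCS as dependent variable. As an example of a mediator it states that "changes in beliefs as measured by the Schema Questionnaire will be the mediator". The criterion is given by citation only: "We will follow the procedures for establishing statistical mediation outlined by" the 1986 source, "using residual gain scores as the measure of change in both the dependent variable and the mediator". The steps are not written out. The paragraph ends with a caution that "the absence of statistical significance may reflect the somewhat limited power with only 50 patients".

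Three other places bear on the point:

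- The power analysis in section 6 "reveals that this study will convey 80% power to detect a group difference in post-treatment BDD-YBOCS scores of" d = 0.78, with 25 per group. It adds that "we will estimate between-group effect sizes of this pilot study to be used in designing future studies". That promise covers between-group effects, not an indirect effect.
- The Primary Aim (section 2) says the study is meant to "collect sufficient pilot data to apply for an externally funded larger-scale research project".
- The Psychological Assessments list (section 5) says of the schema questionnaire: "This scale will assess core beliefs and schemas as potential mechanisms underlying change".

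**The concern.** The causal-steps procedure, as generally applied, asks for three significant results: the total effect of treatment on outcome, the effect of treatment on the mediator (path a), and the effect of the mediator on outcome given treatment (path b). The indirect effect is the product ab. The planned regressions would yield a and b, but the plan does not say that ab will be estimated, tested or given an interval.

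Two things follow. First, the total-effect requirement can turn true mediation into a result of not established even when both paths are significant. That loss comes from the criterion and can be recovered at the same N. It is separate from the sample-size limit that the plan acknowledges. Second, a pass/fail verdict gives the larger project little to plan from, whereas an indirect effect with an interval can be used, even if it is imprecise.

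**Working it through.** **Inputs from the documents.** 50 treated, 25 per arm (section 2, Primary Aim); p < .05 and 80% power at d = 0.78 on post-treatment BDD-YBOCS (section 6, Power analysis); residual gain scores for outcome and mediator (section 6, Mechanisms of improvement). Sidedness is not stated; two-sided is assumed.

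**Assumed, because the documents give no values.** Path a, path b, the slope s of post-treatment on baseline, and unit residual variances.

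**Step 1: the plan's own figure.** 0.78 × √(25/2) = 2.758, and Φ(2.758 − 1.960) = 78.7%. The exact noncentral t gives 77.1%. The stated 80% is reproduced to within rounding by the normal approximation.

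**Step 2: ceiling on the loss.** The requirement cannot cost more than 1 minus the power for the total effect. The plan's d is on post-treatment scores, while mediation uses residual scores. With pre-post correlation r, the effect on the residual scale is D = 0.78/√(1 − r²).

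| r (assumed) | D | Power for total effect | Ceiling on loss |
|---|---|---|---|
| 0 | 0.78 | 77% | 23 points |
| 0.3 | 0.818 | 81% | 19 |
| 0.5 | 0.901 | 88% | 12 |
| 0.7 | 1.092 | 97% | 3 |

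**Step 3: loss at the planned effect.** Trials were simulated with M1 = s·M0 + aT + e and Y1 = s·Y0 + b·(mediator change) + c′T + e, so that d = (ab + c′)/√(1 + b² + s²). Two rules were applied to the same residual gain scores: both paths significant, and both paths plus the total effect significant.

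Example with a = .8, b = .6, s = .5: √(1 + .36 + .25) = 1.269; ab + c′ = 0.78 × 1.269 = 0.990; ab = 0.48; c′ = 0.510. About 48% of the effect is mediated (0.48/0.990).

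Power with / without the total-effect requirement (2,000 trials each, simulation error about 1 point per rate):

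| a, b | s = .5 | s = .8 | s = 1.0 |
|---|---|---|---|
| .5, .4 | 27.0 / 28.7% | 27.0 / 28.1% | 29.2 / 30.0% |
| .8, .6 | 65.4 / 74.3% | 68.6 / 73.3% | 72.4 / 74.8% |
| 1.0, .6 | 77.4 / 90.4% | 83.0 / 90.2% | 85.5 / 89.8% |

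Beyond this grid, paths (.3, .3) lose 0.9, 0.2 and 0.1 points at the three slopes, and (1.3, .6) lose 15.3, 8.8 and 4.8. Hence roughly 0 to 15 points. In a model with no baseline adjustment and unit within-arm SDs, (.78, .5) falls from 74% to 62% and (1.3, .6) from 99% to 77%, a loss of about 22.

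**Step 4: smaller true effects.** Keep a = .8, b = .6, s = .5.

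- d = 0.50: c′ = 0.50 × 1.269 − 0.48 = 0.154. Power is 39% with the requirement and 74% without.
- Complete mediation, c′ = 0: d = 0.48/1.269 = 0.38. Power is 26% and 76%. (Power without the requirement does not depend on c′; 74% and 76% differ only by simulation error.)

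**Step 5: what dropping the requirement costs.** With one path truly null, the false-positive rate per mediator is 0.6–4.0% under causal steps and 4.4–5.6% with a bootstrap interval. The schema questionnaire covers 15 areas. If all were tested separately and were independent, which is an upper range, 1 − (1 − p)^15 goes from 9–46% (p = .006 to .040) to 49–58% (p = .044 to .056). The median interval width is 0.40–0.72 outcome SD, against true indirect effects of 0.14–0.47 SD.

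**The case against.** The strongest objection is that the criticised step is not in the text. The plan cites a procedure and does not spell it out. A reader might infer that the plan demands a significant total effect and will declare mediation absent without one. The documents do not say so, and the cited source cannot be consulted here. The power loss is therefore conditional on how the team applies the method.

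A reader might also take one range of lost points as a property of this trial. The documents give neither path nor the baseline slope, so any range reflects the assumed grid. That objection stands, and it is why the size is given here only as dependent on assumptions.

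The plan's caution tells readers not to treat non-significance as absence of mediation, which softens the harm. But it attributes the problem to the number of patients and supplies no estimate or interval.

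It can also be argued that a stricter rule suits 50 patients and an open list of mediators. This carries less weight: the alternative rule has an error rate of about the nominal 5% per mediator, and the open list is better handled by naming one mediator. It is true that the bootstrap itself adds almost nothing over testing the two paths (74.5% against 74.3% at a = .8, b = .6, s = .5). The gain in power comes from dropping the total-effect step; the bootstrap supplies the interval. The check did not show residual gain scores to be at fault.

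**Conclusion.** The concern holds in a limited form. The text establishes that mediation rests on the causal-steps procedure and that no estimate or interval is specified for the indirect effect. Whether power is also lost depends on the unwritten steps. If a significant total effect is required, the loss at d = 0.78 is roughly 0 to 15 points on baseline-adjusted scores (up to about 22 unadjusted). It is small when baseline strongly predicts outcome and larger when the true effect is below the planned one or mediation is complete. If the step is skipped, the loss is nil.

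The analysis is exploratory and the primary comparison is untouched. This is an improvement to consider, with medium confidence: high for the missing estimate, lower for the size of the power loss.

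**What to change.** Add to section 6, Mechanisms of improvement:

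- A significant total treatment effect is not required for the mediation analysis.
- The indirect effect is reported as the product of the two paths, each from a single regression with baseline mediator and baseline BDD-YBOCS as covariates, with a percentile-bootstrap 95% CI, whatever the p-value of the total effect.
- One main mediator is named in advance; all others are labelled exploratory.

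The cost is SAP wording and a little analysis work, with no new data. Two downsides should be stated openly: the false-positive rate per mediator rises to about nominal, which is the reason for naming one mediator, and the interval will be about as wide as the effect or wider, so it should be presented as a planning range.

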
will take approximately 5 minutes to complete. A detailed assessment schedule is submitted for review.

Psychological Assessments

Comprehensive assessments of BDD symptoms, mood state and cognitions to assess the outcome of therapy will be given at pretreatment, midtreatment, post treatment and at 1- and 6- month follow-up. BDD symptoms, CGI-I score, and depressive symptoms will be assessed every treatment session.

The following instruments will be used and are submitted for review:

(1) Demographic information sheet. This sheet assesses general information such as age, years of education, etc.

(2) Structured Clinical Interview for DSM-IV (SCID; First, Spitzer, Gibbon et al., 1995). This instrument will be used to determine the Axis I psychiatric diagnosis(es).

(3) Structured Clinical Interview for DSM-IV Axis II Personality Disorders (SCID-II; First et al., 1997). Patients will complete the SCID-II self-report questionnaire; for any personality disorder for which the patient's report approaches criterion (number of criteria required minus 1), the rater will administer all interview questions for that personality disorder.

(4) Yale Brown Obsessive Compulsive Scale modified for BDD (BDD-YBOCS). This reliable and valid 12-item semi-structured clinician-administered scale, which was adapted from the Y-BOCS (Goodman et al., 1989), rates current severity of BDD symptoms (Phillips et al., 1997). It will be the study's primary outcome measure. The BDD-YBOCS has excellent interrater and test-retest reliability (ICC for total score=.99 and .88, respectively), internal consistency (Cronbach's alpha=.80), convergent validity ($r=.55$ with the CGI), and sensitivity to change with treatment (Phillips et al., 1997).

(5) BDD-Symptom Scale (BDD-SS) The PI developed the BDD-SS to rate the severity of specific BDD symptoms.

(6) Clinical Global Impression Scale (CGI) This global rating scale, which ranges from 1 (very much improved) to 7 (very much worse) on levels of improvement (CGI-I) and from 1 (normal, not at all ill) to 7 (extremely ill) on severity (CGI-S), is commonly used in pharmacotherapy trials (Guy, 1976). The CGI will be a secondary outcome measure and will also be used to determine clinical deterioration of BDD.

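### The residual gain scores in the mediation analysis are free of their own baseline but not of the other variable's baseline, which usually understates the mediated effect by an amount the documents do not fix

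*Combined protocol and SAP*

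**What the plan says.** Section 6, Mechanisms of improvement, plans a Baron-Kenny mediation analysis by hierarchical regression. On the roles of the variables: "Treatment group (DCS vs. placebo) will be the independent variable, changes in BDD symptom severity (BDD-YBOCS) the dependent variable", and, as an example, "changes in beliefs as measured by the Schema Questionnaire will be the mediator". On scoring, the plan proceeds by "using residual gain scores as the measure of change in both the dependent variable and the mediator", and it justifies this with: "These residual scores will give a reliable estimate of changes in symptom severity and beliefs independent of differences in baseline severity". It promises cautious interpretation, because with 50 patients a null result may come from low power.

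The section does not say whether each score is residualised on its own baseline or on both, whether this is done in the pooled sample or by arm, or whether baselines also enter the mediation models. Elsewhere in section 6, the primary and secondary outcomes are handled by ANCOVA with the pretreatment score as covariate. Both baselines should be available. Section 5, Psychological Assessments, says: "Comprehensive assessments of BDD symptoms, mood state and cognitions to assess the outcome of therapy will be given at pretreatment", and a residual gain score cannot be formed without its baseline.

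**The concern.** A residual gain score is what remains of a later score after regression on the earlier score of the same measure. That removes the measure's own starting level and nothing else. The plan's sentence goes further, because it says that change in beliefs, as well as change in symptoms, is independent of baseline severity. If patients who start more severe hold on to their beliefs more, the belief residual still carries baseline BDD-YBOCS. The symptom residual has had that baseline removed. The two sides of the beliefs-to-symptoms regression are then adjusted for different things, and its coefficient is distorted.

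At stake is the estimated share of any D-cycloserine effect that runs through beliefs, and the chance of detecting it with 50 patients. The plan's caveat would put a null result down to sample size alone, when the scoring rule may have contributed. The trial is meant to supply pilot data for a larger application, so an understated mechanism could be carried forward.

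**Working it through.** **The plan's own figure.** The only power statement concerns the primary comparison: 80% at d = 0.78, 25 per arm, p < .05. Normal approximation, two-sided: Φ(0.78 × √12.5 − 1.96) = Φ(0.798) = 78.7%. The noncentral t gives 77.1%. The figure reproduces approximately. The mediation analysis has no stated figure, so everything below rests on assumed parameters.

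**Inputs.** From the documents: 25 per arm, alpha .05 (two-sided taken as the standard reading), BDD-YBOCS test-retest reliability .88. Assumed, in baseline SD units, with M = beliefs, Y = BDD-YBOCS, 0 = baseline, 1 = later, T = arm:

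- M1 = 0.6·M0 + g·Y0 + a·T + u
- Y1 = 0.5·Y0 + h·M0 + b·M1 + 0.3·T + e
- a = 0.6, b = 0.5, true mediated effect a·b = 0.30; error SD 0.75, so σ² = 0.5625; baseline correlation ρ

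Here g is the effect of baseline severity on later beliefs, and h the effect of baseline beliefs on later severity.

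**What the scores are independent of.** Residualising on own baseline gives

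- rM = a·T + g(Y0 − ρM0) + u
- rY = (0.3 + ab)·T + b·u + (0.6b + h)(M0 − ρY0) + e

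Each is uncorrelated with its own observed baseline (simulated r = 0.00). But cov(rM, Y0) = g(1 − ρ²). At g = 0.15 and ρ = 0.4 this is 0.126. Var(rM) = 0.09 + 0.0189 + 0.5625 = 0.6714, so r = 0.126/0.819 = 0.15, as simulated. It is zero only when g = 0.

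**Effect on the beliefs-to-symptoms path.** In large samples, the coefficient of rM in the regression of rY on T and rM is

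[bσ² − g(0.6b + h)ρ(1 − ρ²)] / [σ² + g²(1 − ρ²)]

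- g = 0: exactly b.
- g = h = 0.15, ρ = 0.4: (0.28125 − 0.02268)/(0.5625 + 0.0189) = 0.445, against 0.50.
- g = 0.15, h = −0.5, ρ = 0.4: (0.28125 + 0.01008)/0.5814 = 0.501.
- g = −0.10, h = 0.15, ρ = 0.5: (0.28125 + 0.016875)/(0.5625 + 0.0075) = 0.523, above b.

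A small further shrinkage arises because arm is not residualised on the baseline. Its expected factor is 48/49 = 0.98. The b path loses about as much at g = 0, so 0.30 × 0.98² = 0.288 even without cross-effects.

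**Simulation** (3,000 to 8,000 trials per setting; power = both paths significant at two-sided .05). The comparator regresses M1 on T, M0, Y0, and Y1 on T, M1, M0, Y0. Its mean mediated effect was 0.294 to 0.302 throughout.

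| g | h | ρ | Mediated effect, residual scores | Shrinkage from 0.30 | Power, residual v one-step |
|---|---|---|---|---|---|
| 0 | 0 | 0.4 | 0.289 | 4% | 68% v 70% |
| 0.05 | 0.05 | 0.4 | 0.281 | 6% | 65% v 69% |
| 0.10 | 0.10 | 0.4 | 0.272 | 9% | 61% v 69% |
| 0.15 | 0.15 | 0.4 | 0.256 | 15% | 56% v 69% |
| 0.30 | 0 | 0.3 or 0.5 | 0.229 | 24% | 52% v 69-71% |
| 0.15 | −0.5 | 0.4 | 0.291 | 3% | 69.6% v 69.2% |
| 0.30 | −0.5 | 0.4 | 0.271 | 10% | 65% v 69% |

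The 1 to 2 point gap in the first row and the 17 to 19 points in the 0.30/0 row move by a point or two between runs. At g = −0.10, h = 0.15, ρ = 0.5, residual scoring gave 0.298 against 0.295 for one-step, so there was no shrinkage.

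A second model with other assumed coefficients (g from −0.2 to 0.35, ρ from 0 to 0.5, h = 0 or −b) gave shrinkage of 2% to 45% relative to one-step, and power changes of +1 to −44 points. The extreme was g = 0.35, ρ = 0.5, h = 0.

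**False positives.** With a = 0 or b = 0, joint rejection was between 3% and 4.5% under both methods, so the power difference does not come from a looser test.

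**The case against.** Four points on the other side have weight.

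- **The sentence is right in a narrow sense.** Each score is uncorrelated with its own observed baseline by construction. A reader might infer that the scores fail to give baseline-independent change at all; the algebra does not support that. The fault lies with the other variable's baseline.
- **The loss is conditional.** A reader might infer that this scoring always biases the paths toward zero. It does not. If symptoms respond to belief change, then h = −b = −0.5, and with a modest g the shrinkage is about 3% with no loss of power. With some opposite signs it vanishes or slightly reverses. The documents give no correlation that would say which setting applies.
- **The two-step reading is inferred.** The plan neither specifies own-baseline residuals nor rules out baseline covariates. It remains the natural reading, and if something else is meant the text needs the same clarification.
- **One-step regression is not unbiased in general.** It recovers 0.30 here because that model generated the data. With an unmeasured common cause of later beliefs and symptoms (SD 0.4), it gave 0.436 and residual scoring 0.391, both too large. With reliability .88 assumed for all scores, it shrank to 0.257.

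The analysis is also exploratory, in a self-described pilot that already promises caution. All of this limits the size and weight of the point. None of it makes the belief residual independent of baseline BDD-YBOCS.

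**Conclusion.** The point holds in conditional form. On the natural own-baseline reading, the plan claims more independence than the scores have, and the usual consequence is an understated mediated effect with some loss of power. The size runs from nothing, through about 15% and 13 points at cross-effects of 0.15/0.15, to about 24% and 17 points (16 to 19 over repeated runs) when baseline severity predicts later beliefs at 0.30. Larger assumed cross-paths give more. These figures rest on assumed paths, error variances and baseline correlations, and should be read as a range.

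A reader might also infer that the efficacy conclusion is at risk. It is not: the primary comparison does not use these scores. This is a low-cost improvement to an exploratory analysis.

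**What to change.** Replace the residual gain scores with one-step regressions on observed scores:

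1. later belief score on treatment, baseline beliefs and baseline BDD-YBOCS;
2. later BDD-YBOCS on treatment, later beliefs, baseline beliefs and baseline BDD-YBOCS.

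Take the mediation paths from these coefficients. Limit the sentence on independence to each score's own observed baseline, or delete it. Add that neither method removes bias from unmeasured common causes of beliefs and symptoms, or from measurement error. If residual scores are kept, state that they are derived in the pooled sample: formed within arm, they would average zero in each arm and erase the treatment effect.

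The cost is wording and about two error degrees of freedom per model (48 to 46 for the belief model, 47 to 45 for the symptom model). In the settings run, one-step regression lost at most about one power point. No new data are needed, and the mediation section would match the ANCOVA used for the main outcomes.
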